Eighth Secondary Endpoint: Proportion of treated patients with an HbA1c improvement of $\geq 0.5\%$ points from baseline at 24 weeks (24 week value minus the baseline value).

Ninth Secondary Endpoint: Proportion of treated participants with an HbA1c improvement of ≥ 0.5 points or more at 24 weeks from baseline and maintained at 48 weeks.

Note: Proportion of treated patients who achieve a HbA1c improvement of $\geq 0.3\%$ or more at 24 weeks from baseline and maintained at 48 weeks. Patients who fail to maintain HbA1c improvement $\geq 0.5\%$ at 48 weeks, for any reason, will be counted as not having achieved this endpoint. Patients who fail to achieve a HbA1c $\geq 0.5\%$ improvement at 24 weeks will be excluded from the tabulation.

Tenth Secondary Endpoint: Change in weight from baseline (post-baseline minus baseline) by visit. Weight change will be reported in both kilograms and %TBWL.

Eleventh Secondary Endpoint: Change in glucose-lowering medication usage.

Twelfth Secondary Endpoint: Change in liver enzyme from baseline at 24 weeks (post-baseline minus baseline) for Alanine Aminotransferase (ALT).

Thirteenth Secondary Endpoint: Change in liver enzyme from baseline at 24 weeks (post-baseline minus baseline) for Aspartate Aminotransferase (AST).

Fourteenth Secondary Endpoint: Change from baseline in blood pressure by visit (systolic and diastolic run separately).

Fifteenth Secondary Endpoint: Change in lipid profile from baseline by visit: total cholesterol

Sixteenth Secondary Endpoint: Change in lipid profile from baseline by visit: triglycerides

Seventeenth Secondary Endpoint: Change in lipid profile from baseline by visit: HDL

Eighteenth Secondary Endpoint: Change in lipid profile from baseline by visit: LDL

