6. ANALYSIS POPULATIONS

Patients will be considered enrolled in the study once the patient has passed endoscopic screening. Screen failures are defined as patient who consented to participate in the clinical study and started the screening tests specified by the protocol but are not subsequently enrolled in the study.

The primary and secondary safety analyses will be performed using the ITT. The primary effectiveness analyses will be performed using the FAS population. The Per-Protocol population and Completed-Cases population will be used for the sensitivity analyses of the primary and secondary effectiveness endpoints.

Intent-to-Treat: The Intent-to-Treat population includes all enrolled patients, regardless of the patient having received the target treatment (at least 6cm of duodenum treated). The point of enrollment occurs when a patient has provided written informed consent and an energy delivery has been attempted during the index procedure.

Full Analysis Set: The FAS population consists of the ITT population patients who received the target treatment (at least 6 cm of duodenum treatment) and that have at least one post-treatment follow-up examination.

Per-Protocol: The Per-Protocol population is a subset of the FAS population and includes all patients who received the target treatment, do not have any major eligibility violations, and maintained stable glucose-lowering medications for 24 weeks post-procedure. The definition of what constitutes a major eligibility violations will be established before the study database is locked.

Completed Cases: The Completed Cases population is a subset of the Per-Protocol population and includes all patients who received the target treatment, do not have any major eligibility violations, and maintained stable glucose-lowering medications for 24 weeks post-procedure, and completed the final Week 48 End of Study Visit.

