7. GENERAL CONSIDERATIONS

Post-text Tables and Listings will be prepared in accordance with the current ICH Guidelines. The header of each Table and Listing will include the sponsor's name and the study number. The information and explanatory notes to be provided in the "footer" or bottom of each Table and Listing will include the following information:

1. Date and time of output generation.
2. SAS® program name, including the path that generates the output.
3. Any other output specific details that require further elaboration.

In general, tables will be formatted with a column displaying findings for all patients combined. Row entries in tables are made only if data exist for at least one (1) patient (*i.e.*, a row with all zeros will not appear). The only exception to this rule applies to tables that list the termination status of patients (*e.g.*, reasons for not completing the study). In this case, zeros will appear for study termination reasons that no patient satisfied. The summary tables clearly indicate the number of patients to which the data apply, and unknown or not performed are distinguished from missing data. Tables, Listings, and Figures will provide the units of measurement, unless there are no units. Results recorded at single times during the study will be presented using the *Level 1* displays for the ITT Population; the example structure is presented below.

Level 1a Display

Parameter and Statistic	Device Generation 1 / 600 Volts / Single Treatment	Device Generation 1 / 600 Volts / Double Treatment	Device Generation 2 / 750 Volts / Double Treatment	All Patients
Age				
Sex				

Level 1b Display

Parameter and Statistic	Device Generation 1 / 600 Volts / Single Treatment	Device Generation 1 / 600 Volts / Double Treatment and Device Generation 2 / 750 Volts / Double Treatment	All Patients
Age			
Sex			

The *Level 2* displays will be used for summarizing the incidence of AEs. An example of the layout for AEs by severity is presented below.

Level 2a Display

System Organ Class Preferred Term	Device Generation 1 / 600 Volts / Single Treatment	Device Generation 1 / 600 Volts / Double Treatment	Device Generation 2 / 750 Volts / Double Treatment	All Patients
SOC PT				

Level 2b Display

System Organ Class Preferred Term	Device Generation 1 / 600 Volts / Single Treatment	Device Generation 1 / 600 Volts / Double Treatment and Device Generation 2 / 750 Volts / Double Treatment	All Patients
SOC PT			

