All mean and median values will be formatted to one more decimal place than the measured value. Standard deviation values will be formatted to two more decimal places than the measured value. Minimum and maximum values will be presented with the same number of decimal places as the measured value.

The number and percentage of responses will be presented in the form XX (XX.X%).

- All summary tables will include the analysis population sample size (i.e., number of patients).
- Relative Study Day 1 is defined as the day the patient underwent the DMR study procedure. All study days are determined relative to the day the patient underwent the DMR study procedure.
- Baseline values will be defined as those values recorded immediately prior to the DMR study procedure.
- Change from baseline for ratio data will be calculated as follows:
$$\text{Change} = \text{Post-Procedure value} / \text{baseline value}.$$
- Change from baseline for differences will be calculated as follows:
$$\text{Change} = \text{Post- Procedure value} - \text{baseline value}.$$
- Missing data may have an impact upon the interpretation of the trial data. However, given the feasibility nature of this study, coupled with the number of patients within a Comparison Set, multiple imputation will not be attempted. The primary presentation of the results will be based on the observed data. A methodology is defined in this section for addressing missing dates.
- Date variables will be formatted as DDMMYY for presentation; SAS Date9. format.
- Months will be converted to days by dividing by 30.42 and rounding up to achieve an integer value.
- SAS® Version 9.4 will be the statistical software package used for all data analyses.
- All data from this study will be presented in a listing.
- Table and listing numbering will follow ICH guidelines for post-text table and listing numbering.

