Proportion of treated patients with an HbA1c improvement of $\geq 0.5\%$ from baseline at 24 weeks (24 week score minus baseline score). Patients who fail to have HbA1c improvement of ≥ 0.5 points from baseline, for any reason, will be counted as not having achieved this endpoint.

Ninth Secondary Endpoint

The distribution of this endpoint is binary. Proportion of treated patients who achieve a HbA1c improvement of $\geq 0.5\%$ or more at 24 weeks from baseline and maintained at 48 weeks. Patients who fail to maintain HbA1c improvement $\geq 0.3\%$ at 48 weeks, for any reason, will be counted as not having achieved this endpoint. Patients who fail to achieve a HbA1c $\geq 0.5\%$ at 24 weeks will be excluded from the tabulation. The primary population for analysis of this endpoint will be the FAS population.

Proportion of treated patients with an HbA1c improvement $\geq 0.5\%$ from baseline at 24 weeks maintained at 48 weeks.

Tenth Secondary Endpoint: The distribution of this endpoint is continuous. The primary population for analysis of this endpoint will be the FAS population. Change in weight from baseline (post-baseline minus baseline) by visit. Weight change will be reported in both kilograms and %TBWL.

Eleventh Secondary Endpoint: Change in glucose-lowering medication usage.

Twelfth Secondary Endpoint: The distribution of this endpoint is continuous. The primary population for analysis of this endpoint will be the FAS population. Change in liver enzyme from baseline at 24 weeks (post-baseline minus baseline) for Alanine Aminotransferase (ALT).

Thirteenth Secondary Endpoint: The distribution of this endpoint is continuous. The primary population for analysis of this endpoint will be the FAS population. Change in liver enzyme from baseline at 24 weeks (post-baseline minus baseline) for Aspartate Aminotransferase (AST).

Fourteenth Secondary Endpoint: The distribution of this endpoint is continuous. The primary population for analysis of this endpoint will be the FAS population. Change from baseline in blood pressure by visit (systolic and diastolic run separately).

Fifteenth Secondary Endpoint: The distribution of this endpoint is continuous. The primary population for analysis of this endpoint will be the FAS population. Change in lipid profile from baseline by visit: total cholesterol

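### SAP Endpoint 9 is labelled a proportion of treated (FAS) patients but is computed among Week 24 responders only, and its Week 48 cut-off is 0.5% in SAP 4.2.1 and 0.3% in SAP 9

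*SAP*

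**What the plan says.** **Label and population.** SAP 4.2.1, 9 and 9.2 all word the Ninth Secondary Endpoint as a proportion of treated participants or patients. SAP 9 assigns it to the FAS. SAP 6 defines that set by treatment and follow-up only: "The FAS population consists of the ITT population patients who received the target treatment (at least 6 cm of duodenum treatment"), plus at least one post-treatment examination. No HbA1c response is required.

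**Exclusion.** Both definitions remove patients who did not reach 0.5% at Week 24. SAP 4.2.1 says that those without this "improvement at 24 weeks will be excluded from the tabulation"; SAP 9 says that those below the cut-off "at 24 weeks will be excluded from the tabulation. The primary population for analysis of this endpoint will be the FAS population".

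**Neighbouring endpoint.** Endpoint 8, the Week 24 response rate, treats the same patients differently. In SAP 9, those who do not improve by 0.5 "points from baseline, for any reason, will be counted as not having achieved this endpoint".

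**Week 48 rule.** Failing to maintain is defined twice:
- SAP 4.2.1: "improvement $\geq 0.5\%$ at 48 weeks, for any reason, will be counted as not having achieved this endpoint"
- SAP 9: "improvement $\geq 0.3\%$ at 48 weeks, for any reason, will be counted as not having achieved this endpoint"

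**Other cut-offs.** The Note under Endpoint 9 in SAP 4.2.1 gives 0.3% as the Week 24 criterion, although the endpoint's heading and the Note's own exclusion sentence use 0.5. The title of Table 14.4.4 in SAP 9.2 also uses 0.3 points.

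**The concern.** A proportion of treated patients answers how many of those treated gained a lasting improvement. A proportion of Week 24 responders answers how often an early improvement persists. Both are reasonable questions, but the second figure is never smaller than the first, and here it would be printed under the first one's name.

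SAP 9.2 asks for overall estimates and group differences in the FAS for this endpoint, and a responders-only rate supplies neither. Because response is observed after treatment, conditioning on it can even reverse the order of the groups.

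The cut-off conflict is a separate fault. Two programmers, one working from SAP 4.2.1 and one from SAP 9, would classify some patients differently. Nothing in the SAP says which section governs, so the choice could be made after the data have been seen.

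**Working it through.** The documents give no expected value, sample-size calculation or power figure for Endpoint 9, so there is no planned number to reproduce.

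**1. Denominator: exact arithmetic, no model.** Let N be the FAS size, R the number improved by at least 0.5% at Week 24, and x the number of those who maintain at Week 48.

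- Quantity in the label: x/N
- Quantity tabulated: x/R
- Ratio: (x/R) ÷ (x/N) = N/R, which is above 1 whenever R < N and x > 0

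Example with N = 20 (the planned enrolment, all assumed to be in the FAS) and assumed R = 13, x = 11:

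| Version | Rate | Exact 95% CI (Clopper-Pearson) |
|---|---|---|
| All FAS | 11/20 = 55% | 32–77% |
| Responders only | 11/13 = 85% | 55–98% |

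N/R = 20/13 = 1.54.

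**2. Group comparison: hypothetical counts.** The SAP's groups have 3, 7 and 10 patients. Suppose 2 of 7 respond and both maintain, while 8 of 10 respond and 6 maintain. Responders only: 2/2 = 100% against 6/8 = 75%. All FAS: 2/7 = 29% against 6/10 = 60%. The order reverses.

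**3. Plausible size.** Inputs:

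- Mean HbA1c reduction, equal at both visits: 0.9 and 1.2 percentage points, the figures Protocol 1.2 cites for a different device; 0.5 is an assumed weaker effect.
- SD 0.8, 1.0, 1.2 and correlation 0.5, 0.6, 0.7 between visits: assumed.
- Bivariate normal reductions D24 and D48: assumed.

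Formulas: P24 = P(D24 ≥ 0.5); all-FAS rate = P(D24 ≥ 0.5 and D48 ≥ t); responders-only rate = all-FAS rate ÷ P24; N/R = 1/P24.

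With t = 0.5:

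| Mean | P24 | All FAS | Responders only | Difference (points) | N/R |
|---|---|---|---|---|---|
| 0.5 | 50% | 33.3–37.3% | 66.7–74.7% | 33.3–37.3 | 2.0 |
| 0.9 | 63.1–69.1% | 47.4–58.1% | 75.1–84.0% | 24.4–29.9 | 1.45–1.59 |
| 1.2 | 72.0–80.9% | 58.2–72.5% | 80.8–89.6% | 16.5–23.9 | 1.24–1.39 |

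**4. Week 48 cut-off.** A patient at 0.6% in Week 24 and 0.4% in Week 48 fails under SAP 4.2.1 (0.4 < 0.5) and succeeds under SAP 9 (0.4 ≥ 0.3). On the same grid, moving t from 0.5 to 0.3 has this effect:

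| Mean | Rise in responders-only rate (points) | Expected patients reclassified in 20 |
|---|---|---|
| 0.5 | 6.2–9.3 | 0.62–0.93 |
| 0.9 | 5.1–6.9 | 0.64–0.96 |
| 1.2 | 4.2–5.0 | 0.60–0.81 |

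**5. Unequal means.** SAP 5.1 has medication optimised after Week 24, so the means may differ. With Week 24 mean 0.9 and Week 48 mean 0.6, 0.9 or 1.2 on the same grid, the difference in step 3 becomes about 20 to 33 points, and the expected reclassified patients about 0.45 to 1.3 in 20.

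**The case against.** The exclusion is stated openly in both sections, so every programmer would obtain the same denominator rule. The FAS can be read as the pool from which responders are drawn, and durability among responders is a legitimate quantity. On that reading only the label needs changing.

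The all-FAS rate can also be recovered. SAP 7 requires that "The summary tables clearly indicate the number of patients to which the data apply" and that "All summary tables will include the analysis population sample size (i.e., number of patients"). At the 0.5% Week 24 cut-off, Endpoint 8 times Endpoint 9 gives (R/N) × (x/R) = x/N. These points limit the harm. They do not make the label true, and they do not help with the cut-offs.

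On the cut-offs, the 0.3% at Week 24 appears in a single sentence of the Note and looks like leftover text, since Protocol section 3 uses 0.3%. Table 14.4.4 is titled by visit and is not tied explicitly to Endpoint 9. Both points are fair, and they make the Week 24 conflict the weaker part. For Week 48, the closing line of the SAP 9 definition and the list in SAP 9.2 lean towards 0.5% but state no separate Week 48 figure, so the conflict stays open.

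The SAP cites protocol Doc. No. 346, whereas the protocol at hand is No. 196. The governing definition therefore cannot be checked, but both faults lie within the SAP itself.

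Finally, this is one of 18 secondary endpoints in a 20-patient feasibility study without formal hypothesis tests, and group results with 3 patients in one group say little. That bears on priority, not on correctness.

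**Conclusion.** Both faults stand on the SAP's current text. Endpoint 9 as defined is a rate among Week 24 responders carrying the name and population of an all-FAS rate, and its Week 48 failure rule has two values.

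The overstatement relative to the label is exactly N/R. Its likely size, 16.5 to 37 percentage points across the three equal-mean scenarios, rests on assumed SDs, correlations and normality and on means borrowed from another device, so it is illustrative only. The cut-off conflict is a matter of text and needs no assumption; its illustrative effect is 4 to 9 points on the reported rate, or roughly one patient or fewer in 20 when the means are equal.

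This should be fixed. No primary or safety result is affected.

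**What to change.** Before database lock:

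1. State one cut-off for Week 24 and one for Week 48, and use them in SAP 4.2.1, 9, 9.2 and the title of Table 14.4.4.
2. Report Endpoint 9 over all FAS patients, counting Week 24 non-responders as failures. Count missing Week 24 values as failures too, as the Endpoint 8 rule implies, and say how this sits with the no-imputation statement in SAP 7.3.1. The Endpoint 9 text does not currently say what a missing Week 24 value means.
3. Show the responders-only rate beside it, labelled as conditional on Week 24 response and with its own denominator.
4. Give the group results required by SAP 9.2 for the all-FAS version.

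The cost is SAP wording and one extra table row, with no new data. The headline durability figure becomes less favourable.

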9.1. Analysis of the Primary Safety Endpoint

Each table number and population will clearly state; results will be presented using the Table 1a design. Results will be tabulated based on the number of patients experiencing one or more device-related or procedure-related serious adverse events at 12 weeks post-procedure.

The statement of the primary research question that will be addressed is as follows:

What percentage of the patients in the ITT population experienced one or more device-related or procedure-related serious adverse events within 12 weeks (84 days) of the index study procedure?

The statement of the secondary research question is specific below:

Is there a difference in the percentage of patients in the ITT population who experienced one or more device-related or procedure-related serious adverse events within 12 weeks (84 days) of the index study procedure based on the generation of the device, voltage, and single vs. double treatment?

The following model will be used to compare the groups identified within each Comparison Set. The dependent variable is the classification of each patient relative to experiencing a device-related or procedure-related serious adverse events at within 12 weeks (84 days) of the index study procedure [variable: DRPRSAE]. Contrast statements will be used to derive the estimates for each pair-wise comparison of a group.

```
PROC GLIMMIX DATA=COMP_SET_1 ;
  CLASS COMP_SET_1_GROUP;
  MODEL DRPRSAE = COMP_SET_1_GROUP / DIST=BINARY LINK=LOGIT
  SOLUTION;
  RANDOM INTERCEPT / SUBJECT=SUBJID_N ;
  LSMEANS TRTAN / DIFF CL;
RUN;
```

Sensitivity analyses will be performed using the FAS and PP populations. Results will be presented in the analysis table 14.4.1 entitled *Summary of the Device-Related or Procedure-Related Serious Adverse Events Within 12 weeks (84 days) of the index study procedure (ITT Population)* and table 14.4.1.1 entitled *Summary of the Device-Related or Procedure-Related Serious Adverse Events Within 12 weeks (84 days) of the index study procedure (FAS Population)* and table 14.4.1.2 entitled *Summary of the Device-Related or Procedure-Related Serious Adverse Events Within 12 weeks (84 days) of the index study procedure (PP Population)*. Listing 16.4.11 entitled *Adverse Events* provides supportive data for Tables 14.4.1, 14.4.1.1, and 14.4.1.2 will be sorted by site number and patient number.

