For Adverse Event reporting, which includes primary and secondary variables, the primary analysis will be based on Patient counts (e.g., the number and percentage of Patients with events among the total number of Patients). The data will be presented in the format of p% (x/N) [e], with p and x being the percentage and number of Patients with events, respectively, N being the sample size of the analysis population, and e being the total number of events occurred in the x Patients. Asymptotic confidence limits will be presented based on the normal approximation to the binomial distribution for differences in proportions. Exact confidence intervals will be used for all other presentations.

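### The SAP 9.1 code comparing groups on the primary safety endpoint cannot give the promised pairwise estimates, and the section 7 interval for differences can have zero width

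*SAP*

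**What the plan says.** SAP 9.1 puts two questions about device- or procedure-related serious adverse events within 84 days. The first is the overall ITT percentage. The second, which is the one at issue, is whether that percentage differs by device generation, voltage and single or double treatment. For this it says: "The following model will be used to compare the groups identified within each Comparison Set". The code opens with "PROC GLIMMIX DATA=COMP_SET_1". CLASS and MODEL contain only the Set 1 group variable, with a binary distribution and logit link. Then come "RANDOM INTERCEPT / SUBJECT=SUBJID_N" and "LSMEANS TRTAN / DIFF CL". The text adds: "Contrast statements will be used to derive the estimates for each pair-wise comparison of a group".

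The section 3 table gives group sizes of 3, 7 and 10. Section 7 defines Comparison Set 1 as all three groups and Set 2 as the group of 3 against the other two combined (17). Section 3 also says that the plan contains the source code for analysing each endpoint.

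Section 7 has a separate interval rule in a paragraph that begins "For Adverse Event reporting, which includes primary and secondary variables". It states: "Asymptotic confidence limits will be presented based on the normal approximation to the binomial distribution for differences in proportions". The next sentence is: "Exact confidence intervals will be used for all other presentations".

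**The concern.** There are two separate faults.

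**The model.** The LSMEANS statement is the only one that asks for all pairwise differences, and it refers to a variable that the model does not contain. The random intercept asks for between-patient variance from data with no within-patient replication. Even with both corrected, a logit model has no finite estimate for a pair in which either group has 0% or 100% events, and groups this small will often have none.

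**The interval rule.** The normal-approximation standard error is zero when both groups are at 0% or 100%. The reported interval then shows complete certainty about a difference that rests on as few as three patients in one group. The rule covers all adverse-event differences, not only the comparison in 9.1.

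No decision depends on either. But without a decision rule, the estimates and intervals are all that the second question produces, and a safety table showing [0, 0] would mislead its reader.

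**Working it through.** **Inputs.** Group sizes 3, 7, 10 and 3 vs 17 come from SAP sections 3 and 7. One binary classification per patient comes from SAP 9.1. The SAP states no event rate, so common rates p of 2, 5, 10 and 20% are assumptions. It gives no confidence level for differences, so 95% is assumed, as in SAP 10.1.3. The plan has no power or precision figure to reproduce; its total does check (3 + 7 + 10 = 20). SAS was not run: the code was read, and the calculations were done in Python.

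**1. Identifiability of the random intercept.** Take illustrative counts 1/3, 2/7, 2/10, fix the random-intercept SD and maximise the integrated likelihood. This is not the SAS estimator; it only shows what the data can distinguish.

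| SD | Log-likelihood | Group 1 vs 3 odds ratio, patient-conditional |
|---|---|---|
| 0 | -11.1015 | 2.00 |
| 1 | -11.1015 | 2.26 |
| 2 | -11.1015 | 2.98 |
| 4 | -11.1015 | 6.05 |

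The fit is identical throughout (33.3, 28.6, 20.0%), while the odds ratio depends on an SD that the data cannot determine.

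**2. Empty groups after the code is repaired.** P(no events in a group of n) = (1-p)^n. At p = 5% this is 0.857, 0.698 and 0.599 for n = 3, 7 and 10, and 0.418 for n = 17.

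- At least one empty Set 1 group: 1 - 0.143 × 0.302 × 0.401 = 98.3%.
- At least two empty, so that all three pairs are lost: 0.240 + 0.155 + 0.060 + 0.358 = 81.3%.
- Set 2 pair lost to an empty group: 1 - 0.143 × 0.582 = 91.7%.

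With q_n = (1-p)^n + p^n, a pair is lost because either group is at 0% or 100% with probability 1 - (1-q_a)(1-q_b).

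| Event | 2% | 5% | 10% | 20% |
|---|---|---|---|---|
| At least one Set 1 group empty | 99.9% | 98.3% | 90.8% | 65.6% |
| At least two Set 1 groups empty | 96.0% | 81.3% | 52.6% | 16.2% |
| Set 2 pair lost to an empty group | 98.3% | 91.7% | 77.4% | 52.3% |
| 3 vs 7 lost (0% or 100%) | 99.2% | 95.7% | 85.9% | 62.1% |
| 3 vs 10 lost (0% or 100%) | 98.9% | 94.3% | 82.4% | 57.2% |
| 7 vs 10 lost (0% or 100%) | 97.6% | 87.9% | 66.0% | 29.5% |

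The loss is pair by pair. With 0/3, 1/7, 2/10, the 7 vs 10 odds ratio is (1/6)/(2/8) = 0.67 (95% limits 0.05 to 9.19), while the estimate for the group of 3 diverges: -11.6, -21.6 and -26.6 after 10, 20 and 25 iterations.

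**3. Width of the difference interval.** The limits are d ± 1.96 × sqrt[p1(1-p1)/n1 + p2(1-p2)/n2]. For 0/3 vs 0/17 both terms vanish.

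- As stated, with no continuity correction: [0, 0].
- With a correction of 0.5 × (1/3 + 1/17): -19.6 to +19.6 points.
- Newcombe: the Wilson upper limits are 3.84/6.84 = 56.1% for 0/3 and 3.84/20.84 = 18.4% for 0/17, giving -18.4 to +56.1 points.
- Exact upper limit for 0/3 under the plan's own rule: 1 - 0.025^(1/3) = 70.8%.

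The probability of zero width is q_a × q_b. At 2, 5, 10 and 20% it is 66.8, 35.9, 12.2 and 1.2% for 3 vs 17, and 70.9, 41.8, 16.7 and 2.3% for 7 vs 10.

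**4. Coverage of nominal 95% limits.** All outcomes are enumerated (4 × 18 for 3 vs 17, 8 × 11 for 7 vs 10), with no continuity correction.

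| True rates | 3 vs 17, normal | 3 vs 17, Newcombe | 7 vs 10, normal | 7 vs 10, Newcombe |
|---|---|---|---|---|
| 20 vs 20% | 75.0% | 95.4% | 90.4% | 96.6% |
| 10 vs 5% | 52.1% | 97.8% | 65.6% | 99.8% |
| 5 vs 10% | 83.2% | 97.1% | 73.2% | 99.8% |
| 5 vs 5% | 98.7% | 93.7% | 99.0% | 99.8% |
| 10 vs 10% | 92.6% | 93.8% | 95.6% | 98.9% |

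The high normal-approximation values at 5 vs 5% arise partly because [0, 0] contains a true difference of zero.

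**The case against.** **No listed table shows a difference in proportions.** The Level 1 and Level 2 displays have group columns and a total, 10.1.3 and 10.1.4 ask for exact intervals on single proportions, and the display named in 9.1 has no pooled column for 17 patients. This is true, but section 7 says that such limits will be presented in adverse-event reporting, primary variable included, and 9.1 asks for a difference in percentages. The [0, 0] result follows from a stated rule.

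**The coding faults would surface when the program is run, and the Set 1 block is a template.** An LSMEANS difference request can stand in for contrast statements, Set 2 needs only new names, and the SOLUTION option might still print each group against a reference. Whether it would survive the LSMEANS error was not tested. Even then it would give two of the three Set 1 pairs, and the random intercept and empty-group problems would remain.

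**Coverage is not poor everywhere.** This stands. It depends on the rates and their direction, as the table shows. The only device data in the documents are no related serious events in 27 patients (protocol Appendix 4), which has an exact upper limit of 12.8% and is indirect because the SAP names a different protocol. At low rates, however, empty groups and zero-width intervals are most likely.

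**Newcombe has its own oddities.** For 1/3 vs 0/17 it gives +0.5 to +79.2 points, excluding zero on a single event, while Fisher's test gives p = 0.15. This is a fair caution about reading such intervals as tests.

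**Conclusion.** The concern holds and is minor. The 9.1 code cannot, as written, supply the promised set of pairwise estimates. Once repaired, it would lose all three Set 1 pairs through empty groups with probability 52.6 to 96.0% at event rates of 10% down to 2%, and 16.2% at 20%. The section 7 rule gives a zero-width interval for 3 vs 17 with probability 66.8% at a 2% rate, falling to 1.2% at 20%, and its coverage can drop to about half when the true rates differ.

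The coding faults and the zero-width result follow from the text and the formula. Their frequencies rest on assumed event rates, on a 95% level and, for the intervals, on no continuity correction. The main primary result and the per-group exact intervals are untouched. SAP 7.1 makes testing informative only, and section 9 says there are no formal hypothesis tests.

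**What to change.** **SAP 9.1.** Remove the GLIMMIX block and the sentences that introduce it, but keep the definition of the outcome variable. Insert: *For each group, x/N with its exact interval, and for each pair of groups in Comparison Sets 1 and 2, the difference in proportions with its 95% interval (section 7), will be presented.*

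**SAP section 7.** Replace the sentence on asymptotic limits with: *Differences in proportions will be presented with 95% Newcombe score intervals.* Note that this governs every adverse-event difference.

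**If the model is kept.** Delete the RANDOM line, put the group variable in LSMEANS in place of TRTAN, state which outcome level is modelled, align the sentence on contrasts with the code and add the Set 2 block. Report no model estimate for any pair in which either group has 0% or 100% events. The model would still give log-odds differences, whereas 9.1 asks about percentages.

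**Cost.** SAP wording and simpler code, with no new data. The intervals will be visibly wide. Newcombe falls slightly short at some rates (93.7% for 3 vs 17 at 5 vs 5%) and is conservative for 7 vs 10 (96.6 to 99.8% at the rates checked). Because it can exclude zero on one event, a note that the intervals are descriptive would help.
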